Study Purpose	To determine the safety and efficacy of serial FMT and fidaxomicin in the treatment of severe or fulminant CDI
Study Design	Prospective, open label, multi-center study
Study Population	Patients with severe or fulminant CDI
Sample Size	30
Dosing	
Each cycle consists of:
 
 1. Serial FMT: 720 cc (1st treatment), 360 cc (2nd Rx), and 180 cc (3rd Rx) of fecal slurry 2. Fidaxomicin: 200 mg oral BID x7-10 days
Masking	None
Study Outcomes	
Primary outcomes
 
CDI resolution, defined as < 3 unformed bowel movements/ 24 hrs or a return to baseline bowel habit, 2 weeks after the last FMT treatment
 
Secondary outcomes
 
 1. Sustained CDI resolution, defined as a lack of CDI recurrence 8 weeks after the last FMT treatment 2. All serious adverse events up to and including week 8. A serious adverse event is any event which results in any of the following after the final FMT: 
 a. Death b. Colonic perforation c. Proven infection related to FMT d. Subsequent hospitalization due to CDI within study period 3. Need for colectomy

	
Exploratory outcomes
 
 1. All direct medical costs for CDI treatment 2. Changes in microbial composition, metabolomics and host immune response after treatment
Inclusion Criteria	
 1. Age > 18 years with severe¹ or fulminant² CDI, without an adequate response to metronidazole IV 500 mg q8H and vancomycin 500 mg PO q6h for at least 2 days or after a single Fecal Microbiota Transplant (FMT). An adequate response is defined as a decrease in stool frequency or inflammatory markers (WBC or C reactive protein) by at least 10% over 48 hours 2. Those with ability to provide informed consent or an alternative decision maker providing consent 
¹- Severe CDI defined as WBC > 15,000 cells/mm³ or serum creatinine level >1.5mg/dL or 1.5x premorbid level ²- Fulminant CDI defined as having any of the following attributable to CDI: Hypotension or shock, ileus, megacolon. An abdominal CT scan should be strongly considered to rule out perforation

Exclusion Criteria	
 1. Those with bowel perforation 2. Those taking chemotherapy or radiation treatment with absolute neutrophil count of < 1000 cells/mm³ 3. Those with colostomy or ileostomy, or colonic strictures 4. Those with subtotal colectomy or planning to have a colectomy 5. Those with significant ileus
Study Duration	Approximately 20 weeks
Study Sponsor	University of Alberta Edmonton, Alberta

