2.0 Objectives

Primary Objectives: To determine the clinical efficacy of combined serial FMT and Fidaxomicin in severe or fulminant CDI 2 weeks after the last FMT

Secondary Objectives:

- a) To determine sustained CDI resolution, defined as a lack of CDI recurrence 8 weeks after the last FMT treatment
- b) To describe serious adverse events up to and including week 8 after the final FMT. A serious adverse event is any event which results in any of the following:
 - i) Death
 - ii) Colonic perforation
 - iii) Proven infection related to FMT
 - iv) Subsequent hospitalization due to CDI within study period
- c) To determine colectomy rate in this patient population

Exploratory Objectives:

- a) All direct Medical costs for CDI treatment
- b) Changes in microbial composition, metabolomics and host immune response after combined serial FMT plus fidaxomicin

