3.5 Intervention and follow up

Patients who fulfill inclusion and exclusion criteria will be screened. Once consent has been obtained, metronidazole and vancomycin will be discontinued and 2L of Golytely will be administered the night prior to FMT. Each participant will undergo a large volume enema of 720cc delivered FMT on day 1, consisting of 200g of donor stool followed by two more days of small volume FMT enema on day 2 (360 cc) and day 3 (180 cc). This constitutes as cycle 1. In the event that a colonoscopy is indicated to rule out other pathology, then the scheduled enema can be delivered at the time of colonoscopy. On day 1, the patient will also start a 7-10 day course of fidaxomicin, as long as no clinical deterioration or complication such as bowel perforation has occurred. Following the first cycle of FMT treatment and fidaxomicin, careful clinical monitoring including vitals, requirement for vasopressors (if applicable), abdominal pain and distension, stool frequency and inflammatory markers including white blood cell (WBC) and C reactive protein (CRP) will be performed daily (Figure 3.0). If the patient has improvement in clinical parameters and inflammatory markers, and has reached a plateau without further changes over 24-48 hours after the first cycle, a second cycle of enema delivery of FMT will be administered. The FMT and fidaxomicin combined cycles will continue until clinical resolution of diarrhea and/or return of inflammatory markers to baseline prior to CDI. At that point, a final FMT 180cc enema will be administered. The maximal number of cycles is 4. At any time when a patient's conditions worsens, the study team will refer patient for surgery.

Each patient will receive FMT from a single donor with multiple collections obtained over time.

Baseline characteristics including age, sex, duration and response to CDI therapy, medical history (including inflammatory bowel disease, irritable bowel syndrome, baseline bowel habit, bowel resection, chemotherapy or radiation, number of CDI in the previous 12 months) and medication use will be collected. Blood work including CBC, electrolytes, creatinine, ALT, ALP, albumin, CRP, INR, HIV, and viral hepatitis serology will be drawn at screening visit (Figure 4.0). In addition, baseline collection of blood, and stool samples will be collected and

biobanked. Repeat stool and blood samples will be collected after each cycle of treatment, and again at week 1, 2, 4 and 8 after the final FMT.

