3.7 Outcome Measures

3.71 Primary Outcome

CDI resolution, defined as < 3 unformed bowel movements/ 24 hrs or a return to baseline bowel habit, 2 weeks after the last FMT treatment

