3.72 Secondary Outcomes

a) Sustained CDI resolution, defined as a lack of CDI recurrence 8 weeks after the last FMT treatment

Clinical status and biological samples will be taken to ensure that CDI has not recurred at 8 weeks

b) Adverse events

All serious adverse events will be recorded up to and including week 8 after the final FMT. A serious adverse event is any event which results in any of the following:

- Death
- Colonic perforation
- Proven infections related to FMT
- Subsequent hospitalization due to CDI within study period

c) Proportion of patients requiring colectomy

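### The synopsis limits serious adverse events to those after the final FMT while sections 2.0 and 3.72 do not, and section 3.6 states no safety follow-up after urgent colectomy

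*Protocol*

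**What the plan says.** Three places in the protocol define serious adverse events. All use the same four results: death, colonic perforation, proven FMT-related infection, and a later admission for CDI.

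- **Synopsis, Study Outcomes, secondary outcome 2.** Collection runs to week 8, with no anchor given for that week. The definition follows: "A serious adverse event is any event which results in any of the following after the final FMT".
- **Section 2.0, secondary objective b.** "To describe serious adverse events up to and including week 8 after the final FMT". The list comes next, with no limit on when the result must occur.
- **Section 3.72 b.** "All serious adverse events will be recorded up to and including week 8 after the final FMT". Again the list carries no time limit.

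The terms for the anchor vary. The efficacy outcomes use one: "2 weeks after the last FMT treatment" in section 3.71 and "a lack of CDI recurrence 8 weeks after the last FMT treatment" in section 3.72 a. The safety window, the visits and the sampling speak of the final FMT.

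Section 3.5 describes repeated cycles of three enemas ("The maximal number of cycles is 4"). For patients who resolve it adds a closing dose: "At that point, a final FMT 180cc enema will be administered". If a patient worsens, "the study team will refer patient for surgery".

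Section 3.6 lists two reasons for discontinuing a patient from the trial: withdrawal of consent and need for urgent colectomy. It does not mention follow-up after either. Colectomy is itself counted as an outcome in section 3.72 c.

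**The concern.** Safety is part of the stated study purpose, and serious adverse events are a secondary outcome. Two analysts with the same data, one working from the synopsis and the other from section 3.72, could report different counts. Under the synopsis, an event during treatment stops counting once the patient receives another FMT.

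The second problem does not depend on how the window is read. Patients who need urgent colectomy are those for whom treatment has failed, and the Introduction itself describes high morbidity and mortality in severe CDI despite medical or surgical treatment. If leaving the trial ends observation, a death after the operation but before week 8 may go unrecorded. The safety summary would then be least complete for the patients at greatest risk.

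**Working it through.** The protocol states no figure to reproduce and no adverse event rate, so the check compares the passages.

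**Step 1: what the final FMT is.** Take it as the last FMT the patient receives. Sections 2.0 and 3.72 use last and final side by side for the same week-8 horizon. Section 3.5 ties follow-up to the final FMT with no exception for patients who do not resolve. Both fit this reading.

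**Step 2: whether there is room for an event before that point.** A cycle has three FMTs. A patient who resolves after one cycle receives 3 + 1 = 4, counting the closing enema. A patient who resolves after four cycles receives 4 × 3 + 1 = 13. Every patient who completes at least one cycle therefore has intervals between FMTs in which an event can occur.

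**Step 3: apply both rules to each listed result.**

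- *Death.* It always follows the last FMT received, so both rules count it.
- *Colonic perforation.* This would ordinarily be a worsening, which section 3.5 sends to surgery. With no further FMT, both rules count it. They differ only if more FMT is given afterwards.
- *Later admission for CDI.* This presupposes discharge. Treatment is given to in-patients, so an admission between cycles is unlikely. The rules will seldom differ.
- *Proven FMT-related infection.* Suppose it occurs after cycle 1 and the patient goes on to cycle 2. Section 3.72 counts it and the synopsis does not. If the infection ends the FMT series, both count it.

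The conflict therefore falls on non-fatal listed events followed by further FMT, and in practice mainly on infection. Infection is also the listed result most directly tied to the donor material.

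**Step 4: urgent colectomy.** Take a treated patient who needs urgent colectomy and dies after the operation, within 8 weeks of the last FMT. Section 3.72 b requires the death to be recorded. Section 3.6 has already discontinued the patient from the trial, and no section says that contact continues. The colectomy is counted under section 3.72 c, but nothing secures capture of the death. Both sections can be followed only if a further statement is added.

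**The case against.** The strongest reply is that the synopsis phrase is a drafting slip. Its first sentence ends at week 8 with no anchor, and the next sentence carries the words that would supply one. The body text is unrestricted. Section 3.5 has adverse events monitored daily in hospital and then weekly to week 8, which implies observation during treatment, and section 5.0 provides an independent data safety monitoring board. All of this stands. Most events should be seen, and the slip is a likely explanation. But the sentence as written still excludes events that section 3.72 counts, and neither monitoring nor the board settles which events enter the outcome.

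It can also be said that a start date for counting is detail a SAP may supply. That is fair, and its absence alone would not be a finding. The contradiction between the synopsis and the body is one.

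On colectomy, section 3.6 does not say that recording stops, and sections 3.5 and 3.72 make no exception. That narrows the point to urgent colectomy and to events after it. It does not resolve the conflict between discontinuing a patient and recording all events to week 8.

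A reader might infer something stronger: that the final FMT means only the closing 180 cc enema, so that a patient who never reaches it could have no countable event, even death. The documents do not support this. Section 3.5 uses the phrase descriptively, and on that reading non-resolvers would have no scheduled follow-up at all. A reader might also size the defect by the share of observation time before the last FMT. Step 3 shows why that misleads: few of the listed events can fall in that time and be followed by more FMT.

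**Conclusion.** The concern holds, within limits. The synopsis contradicts sections 2.0 and 3.72 on which events count. Taking the final FMT as the last one received, the loss is confined to non-fatal listed events followed by further FMT, mainly a proven FMT-related infection. Separately, discontinuation for urgent colectomy conflicts with recording all serious adverse events to week 8, so post-operative deaths and other listed events can be missed.

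Neither part can be given a number. The documents state no serious adverse event rate, no expected number of cycles and no expected number of urgent colectomies among the 30 planned patients. The point should be fixed because safety is a named aim and the remedy is cheap. It is not evidence that on-treatment safety goes unmonitored, and it raises no question about the four-item list, which is the same in all three places.

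**What to change.** - Use one window in the synopsis, section 2.0 and section 3.72: from the first FMT (or first study procedure, if the sponsor prefers) through week 8 after the last FMT received.
- Use that single term in place of last and final throughout, and apply it to every treated patient, with or without a closing enema.
- Report serious adverse events for all patients who received any FMT.
- State in section 3.6 that patients discontinued for urgent colectomy stay in safety and vital-status follow-up to week 8 unless they withdraw consent.

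The first three are wording changes, since monitoring to week 8 is already planned. The fourth adds a few follow-up contacts for each such patient. The reported count may be somewhat higher than under the synopsis wording. No treatment rule changes.

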1.0 Introduction

Clostridium difficile infection (CDI) is the leading cause of hospital-acquired infectious diarrhea, representing a significant healthcare burden worldwide. Severe CDI is associated with a high morbidity and mortality rate despite medical and/or surgical intervention(1). Around 8% develop fulminant CDI resulting in toxic megacolon, multi-organ failure and death (2). In a meta-analysis of primary studies published in 2002 and 2007, the annual cost of CDI in the United States adjusted to 2012 dollars was estimated at \$1.5 billion (3). Recent surveillance data from Alberta Health Services (AHS) found that Edmonton has the highest rate of healthcare associated CDI and the highest CDI mortality in the province of Alberta (Figure 1).

Mild and moderate cases of CDI respond very well to vancomycin, which has recently become the first line therapy(4). Unfortunately, vancomycin is not a narrow spectrum antibiotic, and could also promote the development of vancomycin resistant Enterococcus (VRE) (5). Another antibiotic fidaxomicin, a narrow spectrum antibiotic, is non inferior to vancomycin in clinical efficacy in the treatment of mild to moderate infection and is shown to significantly reduce the rate of CDI recurrence (6); however, the high cost prohibits its use as a first line therapy. Furthermore, it has not been used in treating patients with severe or fulminant CDI. Other therapies including monoclonal antibodies against C Diff Toxin B, bezlotoxumab, have been shown to reduce recurrence in CDI but the mechanism of action and long term effects are still not understood (7). Tigecycline is another broad spectrum antibiotic of the glycylcycline class that has been shown to significantly reduce the toxin production in hypervirulent strains of *C difficile*, however it can lead to further disruption to the gut microbiome (7). Overall these newer therapies are expensive with little knowledge of the mechanism of action in the treatment of CDI (7).

Severe CDI is defined as white blood cell count $> 15,000$ cells/mm³ and fulminant CDI is defined as having any of the following attributable to CDI: hypotension or shock, ileus, and toxic megacolon (4). Severe and fulminant CDI require combined metronidazole with vancomycin; surgical intervention is indicated when medical therapy fails (4).

Fecal microbiota transplantation (FMT), which restores intestinal dysbiosis, is highly efficacious in treating mild to moderate recurrent CDI. There is also emerging evidence that FMT may be effective in severe or fulminant CDI, a situation where the only alternative is colectomy (8). FMT can be administered by difference routes, including enema, colonoscopy and oral capsules (9). However, Health Canada does not allow oral capsule to be administered outside the context of a clinical trial. Although few studies have described the efficacy of FMT in severe and fulminant CDI, it appeared efficacious and safe. For example, our group has successfully treated 6 patients with fulminant CDI with serial FMT plus vancomycin over the past year (Figure 2.0). These patients had avoided colectomy as a result. In addition, Fischer and colleagues demonstrated 17/19 (91%) clinical cure rate in these critically ill patients using combined serial FMT and vancomycin (10). In this protocol, Fischer described using colonoscopy-delivered FMT to treat fulminant CDI after failing at least 5 days of combined metronidazole and vancomycin. At the time of colonoscopy to deliver FMT, if pseudomembranes were noted, vancomycin was restarted for at least 5 days before the second colonoscopic FMT was administered. If pseudomembranes persisted, vancomycin was again given for 5 more days

before the third FMT was administered, and this cycle of FMT and vancomycin continued until pseudomembranes resolved. However, there are questions and uncertainties with this approach. First, vancomycin is not a narrow spectrum antibiotic, and it seems counterintuitive to give FMT and vancomycin at the same time. Second, the presence of pseudomembranes cannot be used for daily clinical monitoring, as it requires an invasive test. Furthermore, it remains unknown how many FMT each patient requires, what the most convenient or safest way to administer the FMT is, what the best strategies for monitoring is, or what the optimal frequency of FMT is. The success of Fischer's protocol thus also highlights the gaps in knowledge in mechanisms of action for FMT in severe or fulminant CDI.

In this prospective, open-label, multi-center study, we aim to determine the efficacy and safety of using a combined serial FMT by enema plus fidaxomicin to treat patients who have severe or fulminant CDI not responding to maximal medical therapy. Our hypothesis is the combination of FMT plus fidaxomicin can reduce the number of FMT required and hospital length of stay compared to FMT plus vancomycin from a historical cohort.

2.0 Objectives

Primary Objectives: To determine the clinical efficacy of combined serial FMT and Fidaxomicin in severe or fulminant CDI 2 weeks after the last FMT

Secondary Objectives:

- a) To determine sustained CDI resolution, defined as a lack of CDI recurrence 8 weeks after the last FMT treatment
- b) To describe serious adverse events up to and including week 8 after the final FMT. A serious adverse event is any event which results in any of the following:
 - i) Death
 - ii) Colonic perforation
 - iii) Proven infection related to FMT
 - iv) Subsequent hospitalization due to CDI within study period
- c) To determine colectomy rate in this patient population

Exploratory Objectives:

- a) All direct Medical costs for CDI treatment
- b) Changes in microbial composition, metabolomics and host immune response after combined serial FMT plus fidaxomicin

3.0 Methods

3.1 Study Design

Prospective, open-label, multi-center study. Sites include:

- University of Alberta Hospital, Edmonton AB

- Foothills Medical Centre, Calgary AB
- Royal Jubilee Hospital, Victoria BC

3.2 Study Setting, Patient Recruitment and Sample Size

In-patients with severe or fulminant CDI who fulfill study criteria will be screened for potential enrollment into this study. We aim to recruit 30 patients over 2 years. As this is a pilot study with a unique patient population, the sample size is based on estimate of patient volume seen previously at all participating sites combined.

3.3 Study Population

Patients admitted to hospital who fulfill the inclusion/exclusion criteria will be considered.

3.31 Inclusion Criteria

- Age > 18 years with severe¹ or fulminant² CDI, without an adequate response to metronidazole IV 500 mg q8H and vancomycin 500 mg PO q6h for at least 2 days or after Fecal Microbiota Transplant (FMT). An adequate response is defined as a decrease in stool frequency or inflammatory markers (WBC or C reactive protein) by 10% over 48 hours
- Those with ability to provide informed consent or an alternative decision maker providing consent

¹- Severe CDI defined as WBC > 15,000 cells/mm3 or serum creatinine level >1.5mg/dL or 1.5x premorbid level

²- Fulminant CDI defined as having any of the following attributable to CDI: Hypotension or shock, ileus, megacolon (4). An abdominal CT scan should be strongly considered to rule out perforation

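### Entry sets no minimum stool count, so some patients can already satisfy the stool-count primary endpoint before any study treatment

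*Protocol*

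**What the plan says.** **Entry.** Protocol Section 3.31 takes adults with severe or fulminant CDI "without an adequate response to metronidazole IV 500 mg q8H and vancomycin 500 mg PO q6h for at least 2 days", or after FMT. Footnote 1 reads "Severe CDI defined as WBC > 15,000 cells/mm3 or serum creatinine level >1.5mg/dL or 1.5x premorbid level". Footnote 2 defines fulminant disease by hypotension or shock, ileus or megacolon, attributed to CDI. Non-response is relative: "An adequate response is defined as a decrease in stool frequency or inflammatory markers (WBC or C reactive protein) by 10% over 48 hours". No criterion states a number of stools.

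**Exclusion.** Section 3.32 removes patients whose ileus is significant. It does not say what makes ileus significant, and it does not mention megacolon.

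**Endpoint.** Section 3.71 defines CDI resolution as "< 3 unformed bowel movements/ 24 hrs", or a return to the patient's usual bowel habit, two weeks after the last FMT. It involves no inflammatory marker, stool test or change from enrolment.

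**Design.** Section 3.1 describes a "Prospective, open-label, multi-center study" and no concurrent control arm. Section 3.2 plans 30 patients.

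**Work-up.** In Section 3.5 the screening tests are blood tests, the list ending "HIV, and viral hepatitis serology will be drawn at screening visit". Baseline stool is collected and stored. The text names no *C. difficile* assay for patients.

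**The concern.** A resolution endpoint measures treatment effect only in patients who have something to resolve on that scale. Here patients are selected on blood markers, haemodynamics or bowel dilatation, while success is judged on stool count. The two need not move together. For a patient who enters with low output, a low count at week 2 may show recovery, persistence of the same state, or nothing at all. This matters most in ileus and megacolon, where few stools can be part of the disease.

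With no concurrent control, such patients are not balanced by similar ones in a comparison arm. They enter the numerator of the headline rate directly. That rate is the trial's only primary result, and a reader would take it as the proportion whose diarrhoea resolved after treatment.

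**Working it through.** **1. Can a patient be eligible and already meet the endpoint?** Take a patient with CDI, white cells above 15,000 and two unformed stools a day, after two days of both drugs.

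- Severity: met on white cells alone.
- Non-response: two stools on both days is a fall of 0%, short of 10%. If white cells and CRP have not fallen by 10% either, response is inadequate.
- Exclusions in Section 3.32: none apply.
- Endpoint: two is below three, so the stool limb is met at enrolment.

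A patient with megacolon, or with ileus judged not significant, can reach the same position through footnote 2. Section 3.5 continues treatment cycles until diarrhoea resolves and/or markers return to baseline. That presumes diarrhoea but does not make it an entry condition.

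**2. The plan's own figure.** There is no calculation to reproduce: "the sample size is based on estimate of patient volume seen previously at all participating sites combined". No target rate, null rate, alpha or power is stated.

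**3. Effect of one such patient.** Let *p* be the probability that the patient would have met the endpoint anyway. If the patient stays below three stools until week 2, the gain in the observed rate is (1 − *p*)/30.

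- *p* = 0 (ceiling): 1/30 = 3.3 points.
- *p* = 0.60 (assumed): 0.40/30 = 1.3 points.
- *p* = 17/19 (the cure proportion that Section 1.0 cites from a series of serial FMT plus vancomycin): (2/19)/30 = 0.35 points.

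**4. Effect of a share *m* of such patients.** Observed rate = *m* + (1 − *m*)*p*, so the inflation is *m*(1 − *p*). Both *m* and the values 0.60 and 0.70 for *p* are assumptions; the documents give no value for *m*.

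| *m* (patients of 30) | *p* = 0.60 | *p* = 0.70 | *p* = 17/19 = 0.895 |
|---|---|---|---|
| 0 (0) | 0.60 | 0.70 | 0.895 |
| 0.10 (3) | 0.64 | 0.73 | 0.905 |
| 0.20 (6) | 0.68 | 0.76 | 0.916 |
| 0.30 (9) | 0.72 | 0.79 | 0.926 |

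At *m* = 0.20 the inflation is 0.20 × 0.40 = 8 points if *p* = 0.60, but 0.20 × 2/19 = 2.1 points if *p* = 17/19. The bias matters most when the treatment works least well.

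**The case against.** **The case against.** Most inpatients with CDI not responding to two drugs probably do have diarrhoea. Excluding significant ileus removes part of the low-output group. The endpoint is read two weeks after the last FMT, so a patient must still be below three stools then. The protocol sets no success threshold, so no formal decision can flip. Figures 3.0 and 4.0 are not available to this review and might list further baseline assessments.

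Much of this stands, and it limits the size. It does not close the gap: significant is undefined, megacolon stays eligible, and neither the eligibility text nor the endpoint text requires the endpoint to be unmet at entry.

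**Stronger readings that the documents do not support.** Because Section 3.31 names no assay, a reader might infer that the trial enrols patients without CDI, and that selecting non-responders to CDI drugs enriches for them. But CDI is itself an entry condition. Footnote 2 requires its features to be attributable to CDI, and patients must already have received CDI drugs or FMT.

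Enrichment also needs non-response to be more likely without CDI than with it. If *f* is the share without CDI, and *r0* and *r1* are the non-response probabilities without and with CDI, the share after selection is *f·r0*/[*f·r0* + (1 − *f*)*r1*]. This equals *f* when *r0* = *r1*. The documents give none of these inputs, and a 10% fall in any one of three markers could arise from ordinary fluctuation. No figure for enrichment can be defended.

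A reader might also infer that patients lose CDI treatment when metronidazole and vancomycin stop. Section 3.5 starts fidaxomicin on day 1. The donor toxin test in Appendix A is product-safety screening and says nothing about how patients are diagnosed.

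**Conclusion.** The point holds for the mismatch between entry and endpoint. As written, a patient can satisfy the stool limb of the primary outcome at enrolment and be counted as resolved without any change, in an uncontrolled study of 30. This follows from the text alone.

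The size is bounded per patient, at no more than 3.3 points each, but unknown in total because the number of such patients is unknown. The ceiling assumes that the patient stays below three stools to week 2 and would otherwise certainly have failed. The table in the working is illustration, not an estimate for this trial.

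The unnamed diagnostic test is a secondary point. An established diagnosis has not been made operational across three sites, which is a gap in wording. It is not evidence that patients without CDI are being enrolled.

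**What to change.** 1. **Record the 24-hour unformed stool count at enrolment**, over a window that ends before the bowel preparation in Section 3.5. Sites already need stool frequency to judge the 48-hour response.
2. **Entrants at 3 or more:** keep the endpoint in Section 3.71 unchanged.
3. **Entrants below 3, including those with ileus or megacolon:** do not count the stool limb alone as resolution. Report them separately, using the clinical parameters and inflammatory markers that Section 3.5 already collects. They remain eligible; a flat entry floor of three stools would remove some of the fulminant patients the trial is meant to study.
4. **Repeat the primary analysis** in patients who did not meet the endpoint at baseline.
5. **Reconcile** footnote 2 of Section 3.31, where ileus qualifies a patient, with Section 3.32, where significant ileus excludes one. Which rule is right is for the investigators.
6. **Secondary:** state in Section 3.31 that CDI is confirmed by a positive *C. difficile* stool test from the current episode, taken from the diagnostic sample. The stored baseline stool is not a substitute, because it follows at least two days of CDI drugs or an FMT, and a negative result there would not disprove CDI.

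**Cost.** One baseline field, a few lines of endpoint and eligibility wording, and one extra analysis. The stool-based rate will rest on slightly fewer patients. Marker data at week 2 may be missing for some, since Section 3.5 allows follow-up by phone.
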